## 1. OBJECTIVES

### 1.1 Study Design

This is a pilot study examining the feasibility of using a molecular endpoint, specifically acquisition of the T790M EGFR resistance mutation, as the primary endpoint for a clinical trial. The study will consist of 20 tyrosine kinase inhibitor (TKI)-naïve patients with mutations in the epidermal growth factor receptor (EGFR). Patients will be treated with the irreversible pan-ErbB TKI compound BIBW 2992, which in pre-clinical studies inhibits the acquired resistance T790M mutant allele and therefore has the potential to delay the emergence of this common resistance mechanism. However, it remains unknown if BIBW 2992 can overcome the T790M mutation in patients. All patients will initially be treated with BIBW 2992 at 40 mg daily, though as in other studies with this compound, dose escalation to 50 mg will be permitted for individual patients after one cycle if there are minimal adverse events at 40 mg. Patients will continue BIBW 2992 until progression, and tumor tissue biopsy for comprehensive genomic profiling is mandatory at the time of acquired resistance. The primary endpoint will be to determine the proportion of patients with T790M resistance mutations at the time of progression. Serial analyses of circulating tumor cells (CTCs) will also be performed to explore the utility of this platform to assess evolving cancer cell genotypes as resistance develops.

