## **12. STATISTICAL CONSIDERATIONS**

### **12.1 Study Design/Endpoints**

This is a pilot study examining the feasibility of using acquisition of a resistance mutation as the primary endpoint for a clinical trial. NSCLC patients with EGFR mutations are highly likely to respond well to EGFR TK inhibition with either first-generation EGFR TKIs (erlotinib, gefitinib) or with the second-generation irreversible inhibitor BIBW 2992, but resistance ultimately develops, see Background. Current literature consistently estimates that fifty percent of resistance to first-generation TKIs is due to the development of a secondary EGFR mutation in exon 20, the point mutation T790M. Since the novel irreversible pan-HER inhibitor BIBW 2992 is highly active in lung cancers harboring activating EGFR mutations and can inhibit the EGFR T790M moiety in pre-clinical studies, a key question is whether BIBW 2992 can suppress the development of clinical resistance via T790M in lung cancer patients.

The study will consist of 24 TKI-naïve patients with mutations in EGFR. Given our relatively large population of referral patients at DF/HCC with EGFR mutations and the collaboration with a few select other centers, This sample size was felt to be feasible to enroll within a three year time period. Each subject will be expected to remain on therapy for approximately 10 months. Therefore within 3.5 years it is expected that we will complete at least 16 of the progression biopsies.

All patients will initially be treated with BIBW 2992 at 40 mg daily, though as in other studies with this compound, dose escalation to 50 mg will be permitted for individual patients after one cycle if there are minimal adverse events at 40 mg. Tumor tissue biopsy for comprehensive genomic profiling is mandatory at the time of acquired resistance (clinical progression). The primary endpoint will be to determine the proportion of patients with T790M resistance mutations at the time of progression. The data collected will be vital in determining the optimal strategy for future studies comparing the efficacy of BIBW 2992 to first-generation EGFR TKIs.

The primary objective is:

1. To determine the proportion of patients that have a T790M mutation on their progression biopsy and to compare this with published data for first-generation EGFR tyrosine kinase inhibitors

The secondary objectives are:

1. To estimate the response rate
2. To estimate the progression-free and overall survival

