## 12.2 Sample Size/Power Calculation for the Primary Endpoint

Based on prior data the rate of T790M at the time of progression on first-generation EGFR TKIs (gefitinib/erlotinib) is 50%.

The null hypothesis is that BIBW 2992 therapy yields the same rate of T790M at the time of progression (50%).

It is expected that approximately 6 of the patients will not undergo a repeat biopsy, despite consenting to the biopsy at the time of enrollment. Reasons for not having a biopsy may include patient withdrawal of consent or not having a lesion that is safe and feasible to biopsy at the time of progression. Therefore, power calculations were performed assuming there would be 18 biopsies performed.

With 18 biopsies and a significance level of 0.05, and using a one-sided binomial test, we can achieve 86% power to detect the alternative hypothesis that BIBW 2992 therapy yields a 20% rate of T790M at the time of progression. The alternate hypothesis implies that BIBW 2992 may be better at suppressing T790M as a mechanism of acquired drug resistance.

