## 12.3 Data to Be Analyzed

Evaluable for the primary endpoint (acquisition of T790M): All patients who undergo a repeat biopsy will be evaluable for acquisition of T790M. If the results of this test are not interpretable due to technical failure of the assay, T790M will be assumed to be present (the more conservative assumption in terms of affecting the primary endpoint). Patients that do not undergo a repeat biopsy will not be included in the primary endpoint analysis.

Evaluable for toxicity. All participants who receive at least one dose of study treatment will be evaluable for toxicity from the time of their first treatment.

Evaluable for objective response. Only those participants who have measurable disease present at baseline, have received at least one cycle of therapy, and have had their disease re-evaluated will be considered evaluable for response. These participants will have their response classified according to the definitions stated below. (Note: Participants who exhibit objective disease progression or die prior to the end of cycle 1 will also be considered evaluable.)

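### Section 1.1 plans 20 patients and Section 12.1 plans 24; of the two, only 24 fits the 18 biopsies behind the stated 86% power

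*Combined protocol and SAP*

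**What the plan says.** The combined protocol and SAP gives the total sample size twice, in sentences of the same form about the same population:

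- Section 1.1 (Study Design): "The study will consist of 20 tyrosine kinase inhibitor" (TKI)-naïve patients.
- Section 12.1 (Study Design/Endpoints): "The study will consist of 24 TKI-naïve patients with mutations in EGFR".

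Section 12.2 builds the power statement on the number of biopsies rather than the number enrolled. It allows for losses ("It is expected that approximately 6 of the patients will not undergo a repeat biopsy"), then says that "power calculations were performed assuming there would be 18 biopsies performed". The test is a one-sided binomial test at 0.05 of a 50% T790M rate against 20%, and the plan concludes that "we can achieve 86% power to detect the alternative hypothesis".

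Section 12.3 fixes the analysis set: "Patients that do not undergo a repeat biopsy will not be included in the primary endpoint analysis".

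**The concern.** A protocol should have one planned sample size, and this one has two. Neither figure is marked as superseded, as a minimum or as an evaluable subset, and no passage says which section governs.

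The difference matters because of the analysis set. With unbiopsied patients left out, enrolment less losses is the number analysed for the primary endpoint. Accrual is also tracked during the trial: under Section 10.2 the safety monitoring committee reviews it, and under Section 4.2 of Appendix 3 sites receive accrual figures so that they can foresee closure. If the trial were closed at the number in its opening design section, it would not be expected to deliver the 18 biopsies on which its only power statement depends.

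**Working it through.** **Inputs.** Enrolment 20 (Section 1.1) or 24 (Section 12.1). From Section 12.2: about 6 patients without a biopsy, 18 biopsies, null rate 0.50, alternative 0.20, one-sided level 0.05, stated power 86%.

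**Step 1: reproduce the stated power.** With n biopsies and X of them T790M-positive, reject when X ≤ c, where c is the largest count with P(X ≤ c | n, 0.5) ≤ 0.05. Power is P(X ≤ c | n, 0.2). For n = 18, c = 5: P(X ≤ 5 | 18, 0.5) = 0.0481 and P(X ≤ 5 | 18, 0.2) = 0.8671. The stated 86% is reproduced, so the power calculation is not at fault.

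**Step 2: see which enrolment gives 18.**

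- 24 − 6 = 18, as in Section 12.2.
- 20 − 6 = 14.
- Reaching 18 from 20 allows only 2 losses (10%), against the 6 that the plan expects.

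**Step 3: exact power for nearby numbers of biopsies.**

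| Biopsies | Reject if X ≤ | Exact level | Power | Losses if 20 enrolled | Losses if 24 enrolled |
|---|---|---|---|---|---|
| 13 | 3 | 0.0461 | 74.7% | 7 | – |
| 14 | 3 | 0.0287 | 69.8% | 6 | – |
| 15 | 3 | 0.0176 | 64.8% | 5 | – |
| 16 | 4 | 0.0384 | 79.8% | 4 | – |
| 17 | 4 | 0.0245 | 75.8% | – | 7 |
| 18 | 5 | 0.0481 | 86.7% | – | 6 |
| 19 | 5 | 0.0318 | 83.7% | – | 5 |
| 20 | 5 | 0.0207 | 80.4% | – | 4 |

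At exactly 6 losses the contrast is 86.7% against 69.8%, a gap of 16.9 points. That overstates the effect of enrolment: power is saw-toothed in n, because c moves in whole steps, and 18 is a local peak.

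**Step 4: compare the two enrolments on the same footing.**

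- *Unweighted mean over 4 to 7 losses.* 20 enrolled: (79.8 + 64.8 + 69.8 + 74.7)/4 = 72.3%. 24 enrolled: (80.4 + 83.7 + 86.7 + 75.8)/4 = 81.7%. Gap 9.4 points.
- *Random biopsy count.* Take the number of biopsies as Binomial(N, r) and average the exact power over it. The rate r is an assumption; 0.75 corresponds to 18 of 24.

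| Assumed r | 20 enrolled | 24 enrolled | Gap (points) |
|---|---|---|---|
| 0.65 | 64.4% | 73.8% | 9.4 |
| 0.70 | 68.5% | 77.5% | 9.0 |
| 0.75 | 72.0% | 80.7% | 8.6 |
| 0.80 | 75.4% | 83.3% | 7.9 |
| 0.85 | 78.8% | 85.5% | 6.7 |
| 0.90 | 81.6% | 87.8% | 6.3 |

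(Gaps are taken from unrounded values.) At r = 0.75 the chance of at least 18 biopsies is 9% with 20 enrolled and 61% with 24.

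**The case against.** The best defence is that Section 12 is the operative statistical section and agrees with itself: 24 enrolled, about 6 lost, 18 biopsies, 86% power. It also gives a feasibility argument for its sample size, which Section 1.1 does not. On that view the fault is one figure in an overview of a self-described pilot, and it does harm only if accrual actually stops at 20, which nothing in the documents says will happen. This is a fair account of the likely cause, and it is why the remedy is small. It does not remove the conflict, because no passage gives Section 12 precedence, and the pilot still carries a formal hypothesis test with a stated power.

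Three narrower points stand in part.

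- The documents favour 24 but do not show which number was approved, so the correction has to be conditional.
- The loss is only approximate, so 23 or 25 would also be arithmetically compatible with 18. The claim is limited to the two figures that the plan states.
- The size of the power gap depends on how losses are modelled. Averaging over 5 to 7 losses gives 69.8% against 82.1%, and over 4 to 8 losses 69.0% against 81.3%, about 12 points each. The direction is the same in every comparison made.

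Section 12.1 also expects at least 16 biopsies within 3.5 years. That is a time-limited lower bound in the paragraph that gives 24. It neither contradicts 18 nor supports 20.

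**Conclusion.** The concern holds. The plan states two different total sample sizes, and its expected loss and biopsy count are consistent with 24 and not with 20. The power statement in Section 12.2 is right for 18 biopsies and needs no change if 24 is confirmed.

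Enrolling 20 instead of 24 would cost about 9 points of power on a like-for-like comparison near the plan's expected loss. The range is about 6 to 9 points when the biopsy count is random at assumed rates of 65% to 90%, about 12 points over the other loss windows tried, and 17 points if exactly 6 patients are lost in both cases. All of these use the plan's 50% and 20% rates and its one-sided 0.05 test. The biopsy rates and the loss windows are assumptions and are not in the documents.

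This must be fixed: it concerns the total sample size behind the primary endpoint, and the correction is close to free.

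**What to change.** Check the approved accrual.

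- **If it is 24:** change 20 to 24 in Section 1.1. Sections 12.1 and 12.2 stand. The cost is one number, with no patients beyond those already planned in Section 12.1.
- **If it is 20:** correct Section 12.1 and restate Section 12.2. With the plan's loss of 6 that means 14 biopsies, rejection at 3 or fewer T790M-positive, exact level 0.0287 and power 69.8%. The cost is a visibly lower stated power.

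In the same edit, say in Section 12.1 how the minimum of 16 biopsies by 3.5 years relates to the 18 used for power. If the analysis were run at 16, the power would be 79.8%.

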### 1.2 Primary Objective

1. To determine the proportion of patients that have a T790M mutation on their progression biopsy and to compare this with published data for first-generation EGFR tyrosine kinase inhibitors

### 1.3 Secondary Objectives

1. To estimate the response rate
2. To estimate the progression-free and overall survival
3. To describe the safety of obtaining repeat tumor biopsies for genotype analysis
4. To describe other mechanisms of resistance (besides T790M) observed on the progression biopsies
5. To explore the results of experimental CTC-derived genotype assessed from serial blood samples taken during therapy with BIBW 2992 and to compare CTC-derived results with those from the progression biopsies

## 2. BACKGROUND

### 2.1 Study Agent

#### 2.1.1 Scientific Background

BIBW 2992 is a highly selective and potent low molecular weight, irreversible inhibitor of the erbB-family of tyrosine kinase receptors EGFR (erbB1 / HER1) and HER 2 (erbB2). The potency of BIBW 2992 was determined in enzymatic assays using recombinant human wild-type EGFR (IC50 0.5 nM) and HER2 (IC50 14 nm) (ref. investigator's brochure). A panel of recombinant human kinases tested in parallel was not inhibited, demonstrating the high target specificity of BIBW 2992. Molecular

CONFIDENTIAL

This document is confidential. Do not disclose or use except as authorized.

modeling revealed that BIBW 2992 binds covalently and with high affinity to Cys773 within the catalytic cleft of the ATP-binding pocket of the EGF receptor. It has been reported that this specific molecular interaction results in irreversible inhibition of the EGFR tyrosine kinase domain. Experimental data from *in vitro* washout studies confirmed the irreversible binding of BIBW 2992 to its molecular target. In constitutively EGFR-overexpressing A431 human epidermoid cancer cells, BIBW 2992 inhibition of EGFR-signaling lasted for up to 7 hours after removal of the compound from the cell cultures (ref. investigator's brochure). In contrast, A431 cells exposed to reversible EGFR TKIs regained full receptor function almost immediately after inhibitor washout.

The efficacy and potency of BIBW 2992 was demonstrated *in vitro* in receptor phosphorylation and cell proliferation assays in various human cancer cell models.

The specific activity of BIBW 2992 was determined in two independent *in vitro* assay systems: i) EGF-induced EGFR autophosphorylation using immunoprecipitation and Western blot and ii) clonogenic, anchorage-independent cell growth in a soft-agar assay system. The antiproliferative effects observed with BIBW 2992 compare favorably to activity data published for gefitinib in the same NSCLC cell models. In addition, BIBW 2992 suppressed EGFR phosphorylation and clonogenic growth in the gefitinib resistant NCI-H1975 model, suggesting that tumour cells harboring the T790M EGFR TKI resistance mutation remain sensitive to this irreversible EGFR small molecule inhibitor.

*In vitro* activity of BIBW 2992 in human cancer cell models is noted in Table 1 below.

CONFIDENTIAL

This document is confidential. Do not disclose or use except as authorized.

**Table 1** *In vitro* activity of BIBW 2992 in human tumour cell models expressing wild type or mutated EGFR

Cell line	Origin	EGFR status	BIBW 2992 IC 50		Gefitinib IC 50	
			EGFR-phosphorylation 	Proliferation in vitro 	EGFR-phosphorylation 	Proliferation in vitro 
NCI-H1666	NSCLC	Wild-type	7 nM	16 nM	100 nM	4 $\mu$ M
NCI-H3255	NSCLC	L858R-mutation	6 nM	0.7 nM	50 nM	63 nM
NCI-H1975	NSCLC	L858R-mutation and T790-resistance mutation	93 nM	99 nM	resistant	resistant

1 EGF induced auto-phosphorylation of EGFR

2 clonogenic anchorage-independent soft agar assay

3 MTS assay (R06-1388)

The *in vivo* activity of BIBW 2992 against EGFR was investigated in an A431 subcutaneous xenograft model (ref investigator's brochure). Daily oral treatment with BIBW 2992 at doses of 20 mg/kg resulted in an almost complete inhibition of tumor growth over a period of 25 days. Similar anti-tumor activity was observed in NCI-N87 tumor bearing mice treated with BIBW 2992 at similar concentrations. In these *in vivo* studies, BIBW 2992 plasma concentrations of 80-285 nM corresponding to an AUC0-24 of 589-3198 nM\*h were required for anti-tumor activity. All BIBW 2992 doses shown to be effective in mouse xenograft models were well tolerated.

### 2.1.2 Pharmacology and Toxicology Profile

The absolute bioavailability of BIBW 2992 after oral ingestion was 45% in rats with a median tmax reached after 4 hours and a terminal half-life (t1/2) of 4.5 hours. In rats the exposure was dose proportional and no gender-related effects or compound accumulation was observed. BIBW 2992 is primarily excreted via the feces. No relevant inhibition of cytochrome P450 isoenzymes was found. *In vitro* BIBW 2992 is however a CYP3A4 substrate. Since this is not considered a dominant metabolic pathway, *in vivo* drug-drug interactions with CYP3A4 inducers or inhibitors are not expected (ref investigator's brochure).

*In vivo* BIBW 2992 was metabolized only to a minor extent and the metabolism was governed by adduct formation to proteins or nucleophilic small molecules. It was found that metabolism is of subordinate role for BIBW 2992 and that enzyme-catalyzed metabolic reactions play a negligible role for the metabolism of BIBW 2992 *in vivo*. Only approx. 2 % of the doses were metabolized by FMO3 *in vivo*. The CYP3A4-dependent N-demethylation was even too low to be quantitatively detected in human volunteers. Therefore, intrinsic (e.g. genetic predisposition) or extrinsic (e.g. by comedications)

CONFIDENTIAL

This document is confidential. Do not disclose or use except as authorized.

effects on the activity of FMO3 or CYP3A4 *in vivo* are expected to be of little, if any, relevance for the pharmacokinetics of BIBW 2992.

The human ADME data confirmed the results of the preclinical [C] ADME studies and all metabolites of the human [C] ADME study were observed in the rat or the minipig. In acute toxicology studies, oral administration of single doses in rats and mice indicated a low acute toxic potential of BIBW 2992. Changes in renal and hepatic function occurred only at doses that were 10-30 fold above the levels required for antitumour activity. BIBW 2992 had effects on gastrointestinal function that were dose-dependent and in high doses, leading to profound inhibition. No acute toxic effects on the central nervous system were detected.

In oral repeated dose studies for up to 26 weeks in rats and minipigs, the main target organs were the gastrointestinal tract (rats and minipigs), kidneys (rat), and the skin (rats). In the gastrointestinal tract, increasing systemic exposure was associated with dose-dependent atrophy of the epithelium and concomitant focal erosions/ulcerations in the stomach of rats and minipigs. Clinically this resulted in diarrhea in both species and fecal occult blood in a single minipig. In rat kidneys papillary necrosis and dilated tubules were found. Similar pathologic findings, i.e., papillary necrosis in rats and dogs have been described previously for the EGFR-small molecule inhibitor gefitinib. However, nephrotoxicity has not been reported as a side-effect of gefitinib therapy in humans. A secondary pathophysiologic effect on renal function in BIBW 2992-treated animals due to diarrhea-induced dehydration and emaciation has to also be considered. Cutaneous alterations, i.e., epithelial atrophy were observed in rats. However, BIBW 2992 is not irritating to intact skin in albino rabbits and the effects observed in rats are most likely related to the specific pharmacodynamic mechanism of EGFR-inhibition (ref investigator's brochure). A variety of organs including the aerodigestive tract and reproductive organs were affected by epithelial atrophy. These atrophic changes were not severe and fully reversed during a 2-week recovery period. Minor cardiovascular effects (increased blood pressure and heart rate) and a dose-dependent decrease of QT time in the electrocardiogram (ECG) occurred in BIBW 2992-treated minipigs. These data do not indicate a risk for QT-prolongation related arrhythmia. BIBW 2992 had no pro-arrhythmic potential, as determined by the effects on HERG-mediated potassium current or on guinea pig papillary muscle action potential configuration. BIBW 2992 demonstrated mutagenic potential in bacteria but had no genotoxic potential *in vivo* even at highly toxic/lethal doses in animals. Because of its specific pharmacodynamic mechanism of action, BIBW 2992 is potentially embryo/fetotoxic and/or teratogenic.

### 2.1.3 BIBW 2992 Clinical Trial Program

The most up to date trial and safety information can be found in the current version of the Investigator Brochure.

BIBW 2992 showed moderately fast absorption with median  $t_{max}$  values between 1 h to 6 h after administration. The gMean terminal half-life ( $t_{1/2}$ ) of BIBW 2992 mainly ranged between 13 h to 57 h. In general, the maximum blood concentration ( $C_{max}$ ) and the integral of the concentration time curve (AUC) of BIBW 2992 increased in a dose-proportional way.

The maximum tolerated dose (MTD) of BIBW 2992 was identified as 50 mg once daily in phase I continuous dosing monotherapy trials. The 50 mg dose is currently used in the phase IIb/III trial 1200.23 in NSCLC patients progressing on erlotinib or gefitinib, as maximum EGFR inhibition is required in this last-line population enriched for the presence of resistance mutations. For a more

CONFIDENTIAL

This document is confidential. Do not disclose or use except as authorized.

sensitive population with EGFR activating mutation, a starting dose of 40 mg is expected to be sufficient. In phase I clinical trials of BIBW 2992, durable responses (>20 months) were seen at daily doses of 40 mg and less.

In this trial, a starting dose of 40 mg will be used in order to optimize the efficacy/toxicity balance in the very sensitive population of TKI-naïve patients with EGFR mutations. Variability is expected in the incidence and severity of adverse events and to ensure maximum EGFR inhibition, dose escalation to 50 mg will be allowed after the first course of treatment (28 days) in patients with minimal treatment-related adverse events. This dose escalation strategy has been used before, particularly in the ongoing large international phase III randomized trial of BIBW 2992 versus chemotherapy in patients with EGFR mutations (LUX-Lung 3).

The Adverse Events (AEs) observed to date in Phase I and Phase II trials are consistent with those reported for other EGFR tyrosine kinase inhibitors (dose dependent diarrhea and skin-related adverse events including rash and acne). Other AEs were in the expected range for patients with advanced cancer disease (ref investigator's brochure). In the BIBW 2992 Phase I monotherapy trials, the most frequent drug-related adverse events were associated with gastrointestinal disorders (diarrhea, nausea, vomiting, stomatitis), skin and subcutaneous tissue disorders (rash, dry skin, pruritus, acneiform rash, and acne), general disorders and administration site conditions (fatigue, mucosal inflammation), respiratory disorders (epistaxis, typically grade 1), and metabolism and nutritional disorders (anorexia, dehydration).

Diarrhea is the single most often reported gastrointestinal AE. An increased incidence of diarrhea grade 3 has been observed in phase II monotherapy trials (starting dose of 50 mg qd). Prompt and proactive management of diarrhea together with timely treatment pause and dose reduction is crucial to reduce the severity of diarrhea and its potential complications such as dehydration leading to serum electrolyte changes (hyponatraemia, hypokalaemia and hypomagnesaemia) and/or renal impairment.

Nausea and vomiting are the other commonly reported gastrointestinal adverse events and can be generally managed successfully with the use of antiemetics.

Skin related adverse events present in a number of forms, i.e., rash (including erythematous, maculopapular, papular, etc.), acne, dermatitis acneiform, dry skin, skin reaction and pruritis. Folliculitis as well as nail changes (including paronychia) are other reported manifestations of skin-related adverse events with BIBW 2992. Early and adequate management of skin-related adverse events can reduce the frequency and the severity of them.

Further AEs included oral discomfort (stomatitis, mouth ulceration, oral pain, dry mouth, soft tissue disorder) and mucosal inflammation. Conjunctivitis and rhinorrhea as a result of inflammation in the mucosal membranes have been reported. Mucosal and skin dryness can lead to epistaxis, which has to date been observed at CTCAE Grade 1. Anorexia, fatigue and asthenia are also frequently observed.

Of 22 evaluable patients with NSCLC from Phase I trials with BIBW 2992, there have been four partial responses (PRs) (3 confirmed and 1 unconfirmed PR) ranging in duration from 5 months to 24 months. All 4 patients were non-smoking Caucasian with adenocarcinoma of the lung. In two of these three patients with confirmed PR, EGFR sequencing has shown exon 19 in-frame deletions.

The efficacy and safety of BIBW 2992 in NSCLC patients with EGFR mutations is under evaluation in a phase II trial (LUX-Lung 2). In this trial, patients with Stage IIIB/IV lung adenocarcinoma with

EGFR mutation in exons 18-21 and failure of one line of systemic chemotherapy were treated with BIBW 2992 at a dose of 50 mg once daily until disease progression. The trial underwent two major amendments. The first was to decrease the starting dose to 40 mg once daily and the second was to allow inclusion of chemotherapy-naïve patients. 129 patients were enrolled. Preliminary results were presented in August 2009 at the World Congress on Lung Cancer. The response rate was 63% in the first-line patients and 66% in the second-line patients. Diarrhea and skin-related adverse events have been the main side effects but have been manageable with appropriate dose interruption/reduction. The incidence of grade 3 diarrhea was lower at 40 mg (4.3%) than at 50 mg (30%). Survival data are not yet mature for analysis.

A global, randomized, phase III trial (LUX-Lung 3) is currently ongoing and is assessing the progression-free survival difference between first-line BIBW 2992 and first-line chemotherapy with cisplatin and pemetrexed in NSCLC patients with EGFR mutations.

